10.3 Change in Height SDS

HT SDS will be summarized with descriptive statistics at the end of OLE years 1 - 4 and for each year on PEN. HT SDS will also be presented for each treatment year, including Period I and II, by the original treatment group assignment and total. In addition, HT SDS will be summarized by ADA status. Descriptive statistics will be used to characterize the change in HT SDS. The change in HT SDS will be calculated from baseline of Period I, as well as each 12 month period.

In addition, the cumulative change in HT SDS from the baseline at Period I will be calculated for each of the scheduled Month 12 visit of each year, using the original treatment groups assignment and total.

10.4 Bone Maturation

BM will be evaluated as the BA divided by the chronological age (CA).

BM = BA/CA

BA is reported as year and months, and will be converted to a decimal value as years + months/12.

CA will be calculated as (date of BA assessment – Birth date)/365.25.

BM will be calculated at 12 month intervals. The change in BM will be calculated as the change in BA/change in CA for each of the intervals defined for the calculation of HV, when the BA assessment is available. Descriptive statistics will be used to characterize the change in BM.

10.5 Pubertal Status

The pubertal status will be reported at the end of each year of the OLE and PEN periods.

11 LIST OF TABLES AND DATA LISTINGS

11.1 Tables

Table No.	Description
2.1	Overall Summary of patients with treatment-emergent adverse events (Safety Analysis Set)
3.1	Summary of treatment emergent adverse event (All causality) in >= 2% of patients (Safety Analysis Set)
3.1b	Summary of treatment emergent adverse event (All causality) in >= 5% of patients (Safety Analysis Set)
4	Summary of Somatrogon Patient Disposition - CP-4-004 OLE
4.1	Summary of AESI - CP-4-004 OLE (Safety Analysis Set)
5.1	Summary of treatment-emergent serious adverse events (All Causalities) (Safety Analysis Set)
6	Summary of Antibody Titers Overall and by Year: Full Analysis Set
10	Annualized Height Velocity at End of each OLE and PEN Year by ADA Status: Full Analysis Set
11	Highest IGF-1 SDS During OLE and PEN Years by ADA Status: Full Analysis Set

Table No.	Description
20	Adverse Events of Special Interest in PEN Years: Full Analysis Set
1.2.2	Height SDS at Baseline and End of Main Study, End of OLE and PEN Years by Initial Cohort Assignment: Full Analysis Set
1.2.2.1	Cumulative Change in Height SDS at End of Main Study, End of OLE and PEN Years by Initial Cohort Assignment: Full Analysis Set
1.2.3	Highest IGF-1 SDS During OLE and PEN Years: Full Analysis Set
14.1.1.1	Disposition of Patients – Year 1 OLE
14.1.1.2	Disposition of Patients – OLE Years 2-4 and PEN
14.1.2.1	Demographics at Start of OLE (Year 1): Full Analysis Set
14.1.2.2	Demographics at Start of Years 2-4 and PEN: Full Analysis Set
14.1.3	Medical History at Start of Main Study: Full Analysis Set
14.1.4.1	Characteristics at Start of OLE (Year 1): Full Analysis Set
14.1.4.2	Weight, Height, and BMI at Start of OLE Years 2-4 and PEN Years: Full Analysis Set
14.2.1.1	Annualized Height Velocity at End of OLE Years: Full Analysis Set
14.2.1.2	Annualized Height Velocity on PEN: Full Analysis Set
14.2.1.3	Annualized Height Velocity (cm/yr) at End of Main Study, End of each OLE and PEN Year by Initial Cohort Assignment: Full Analysis Set
14.2.2.1	Height SDS at End of OLE and PEN Years: Full Analysis Set
14.2.2.2	Height SDS at Baseline and End of Main Study, End of each OLE and PEN Year by Initial Cohort Assignment: Full Analysis Set
14.2.3.1	Annual Change in Height SDS at End of each OLE Year: Full Analysis Set
14.2.3.2	Annual Change in Height SDS at End of each PEN Year: Full Analysis Set
14.2.3.3	Cumulative Change in Height SDS at End of Main Study, End of each OLE and PEN Year by Initial Cohort Assignment: Full Analysis Set
14.2.4.1	Bone Age at End of each OLE and PEN Year: Full Analysis Set
14.2.4.2	Bone Maturation Change at End of each OLE Year: Full Analysis Set
14.2.4.3	Bone Maturation Change at End of each PEN Year: Full Analysis Set
14.3.1.1	Overall Summary of Patients with Treatment-Emergent Adverse Events: Full Analysis Set
14.3.1.2	Overall Incidence of Treatment-Emergent Adverse Events by SOC and Preferred Term: Full Analysis Set
14.3.1.3	Overall Incidence of Serious Treatment-Emergent Adverse Events by SOC and Preferred Term: Full Analysis Set
14.3.1.4	Overall Incidence and Severity of Treatment-Emergent Adverse Events by SOC and Preferred Term: Full Analysis Set
14.3.1.5	Overall Incidence and Relationship of Treatment-Emergent Adverse Events by SOC and Preferred Term: Full Analysis Set
14.3.1.6	Overall Incidence of Treatment-Emergent Adverse Events that Lead to Withdrawal from the Study by SOC and Preferred Term: Full Analysis Set

Table No.	Description
14.3.2.1	Annual Incidence of Treatment-Emergent Adverse Events by SOC and Preferred Term: Full Analysis Set
14.3.2.2	Annual Incidence of Serious Treatment-Emergent Adverse Events by SOC and Preferred Term: Full Analysis Set
14.3.2.3	Annual Incidence and Severity of Treatment-Emergent Adverse Events by SOC and Preferred Term: Full Analysis Set
14.3.2.4	Annual Incidence and Relationship of Treatment-Emergent Adverse Events by SOC and Preferred Term: Full Analysis Set
14.3.2.5	Annual Incidence of Treatment-Emergent Adverse Events of Special Interest by Preferred Term: Full Analysis Set
14.3.4.1	Overall Incidence of Injection Site Reactions by SOC and Preferred Term: Full Analysis Set
14.3.4.2	Annual Incidence of Injection Site Reactions by SOC and Preferred Term: Full Analysis Set
14.3.4.3	Overall Summary of Injection Site Pain, Redness, Bruising, Swelling, and Itching Score: Full Analysis Set
14.3.4.4	Annual Summary of Injection Site Pain, Redness, Bruising, Swelling, and Itching Score: Full Analysis Set
14.3.5.1	Summary of IGF-1 SDS at End of each OLE and PEN Year: Full Analysis Set
14.3.5.2	Summary of IGF-1 SDS >2 by Year: Full Analysis Set
14.4.1	Summary of Antibody Titers Overall and by Year: Full Analysis Set
14.4.2.1	Annualized Height Velocity at End of OLE and PEN Years by ADA Status: Full Analysis Set
14.4.2.2	Annualized Height Velocity on PEN by ADA Status: Full Analysis Set
14.4.2.3	Annualized Height Velocity (cm/yr) at End of Main Study, End of each OLE and PEN Year by ADA Status and Initial Cohort Assignment: Full Analysis Set
14.4.2.4	Height SDS at End of each OLE and PEN Year by ADA Status: Full Analysis Set
14.4.2.5	Height SDS at Baseline and End of Main Study, End of each OLE and PEN Year by ADA Status and Initial Cohort Assignment: Full Analysis Set
14.4.2.6	Annual Change in Height SDS at End of each OLE Year By ADA Status: Full Analysis Set
14.4.2.7	Annual Change in Height SDS at End of each PEN Year by ADA Status: Full Analysis Set
14.4.2.8	Cumulative Change in Height SDS at End of Main Study, End of each OLE and PEN Year by ADA Status and Initial Cohort Assignment: Full Analysis Set
14.4.2.9	Highest IGF-1 SDS During OLE and PEN Years by ADA Status: Full Analysis Set
14.4.3.1	Annual Incidence of Treatment-Emergent Adverse Events by SOC and Preferred Term by ADA Status: Full Analysis Set
14.4.3.2	Annual Incidence of Serious Treatment-Emergent Adverse Events by SOC and Preferred Term by ADA Status: Full Analysis Set
14.4.3.3	Annual Incidence and Severity of Treatment-Emergent Adverse Events by SOC and Preferred Term by ADA Status: Full Analysis Set
14.4.3.4	Annual Incidence and Relationship of Treatment-Emergent Adverse Events by SOC and Preferred Term by ADA Status: Full Analysis Set

Table No.	Description
14.4.3.5	Annual Incidence of Treatment-Emergent Adverse Events of Special Interest by Type and Preferred Term by ADA Status: Full Analysis Set
14.4.3.6	Overall Incidence of Injection Site Reactions by SOC and Preferred Term by ADA Status: Full Analysis Set
14.4.3.7	Annual Incidence of Injection Site Reactions by SOC and Preferred Term by ADA Status: Full Analysis Set
14.5.1.1	Laboratory Test Results – Glucose Metabolism: Full Analysis Set
14.5.1.2	Laboratory Test Abnormal Results – Glucose Metabolism: Full Analysis Set
14.5.2.1	Laboratory Test Results – Endocrinology: Full Analysis Set
14.5.2.2	Laboratory Test Abnormal Results – Endocrinology: Full Analysis Set
14.5.3.1	Laboratory Test Results – Lipid Metabolism: Full Analysis Set
14.5.3.2	Laboratory Test Abnormal Results – Lipid Metabolism: Full Analysis Set
14.5.4.1	Laboratory Test Results – Clinical Chemistry: Full Analysis Set
14.5.4.2	Laboratory Test Abnormal Results – Clinical Chemistry: Full Analysis Set
14.5.5.1	Laboratory Test Results – Hematology: Full Analysis Set
14.5.5.2	Laboratory Test Abnormal Results – Hematology: Full Analysis Set
14.5.6.1	Laboratory Test Results – Urinalysis: Full Analysis Set
14.5.6.2	Laboratory Test Abnormal Results – Urinalysis: Full Analysis Set
14.5.7	Laboratory Test Results – Increases in ALT, AST, and Total Bilirubin: Full Analysis Set
14.6.1	Vital Signs by Visit and Change from Start of OLE: Full Analysis Set
14.6.2	Physical Examination Abnormalities by Visit: Full Analysis Set
14.6.3.1	ECG Results by Visit and Change Within Each Year: Full Analysis Set
14.6.3.2	Electrocardiogram (ECG) Abnormal Shifts by Year: Full Analysis Set
14.6.4	Concomitant Medications Within Each Year by ATC2 and Preferred Term: Full Analysis Set
14.7.1	Total Duration of Treatment: Full Analysis Set
3.1.1	Summary of treatment emergent adverse event (All causality) by SOC and PT (Safety Analysis Set)
6.1.1	Summary of treatment-emergent adverse events leading to study drug withdrawn (All Causalities) (Safety Analysis Set)
6.1.2	Summary of treatment-emergent adverse events leading to study drug reduction or interruption (All Causalities) (Safety Analysis Set)
6.1.3	Summary of treatment-emergent adverse events leading to study discontinuation (All Causalities) (Safety Analysis Set)
OC15.4	Annual Incidence and Severity of Treatment-Emergent Adverse Events by SOC and Preferred Term: Full Analysis Set
OC15.6	Annual Incidence and Relationship of Treatment-Emergent Adverse Events by SOC and Preferred Term: Full Analysis Set

11.2 Listings

Listing No.	Description
16.1.7	Randomization
16.2.1.1	Patient Disposition
16.2.1.1b	Patient Disposition - CP-4-004 OLE
16.2.1.1c	Listing of Patients final height as of last known visit in Study CP-4-004
16.2.1.2	Trial Inclusion/Exclusion Criteria
16.2.1.3	Inclusion/Exclusion Criteria Not Met
16.2.10	Comments
16.2.2	Protocol Deviations
16.2.4.1	Patient Demographics
16.2.4.2	Medical History at Start of Main Study
16.2.4.3	ACTH Test Results
16.2.4.4	MRI Results
16.2.4.5	Pubertal Status at Start of OLE (Year 1)
16.2.5.1	Patient Visits
16.2.5.2	Drug Accountability
16.2.6.1	Height, Height SDS, Change in Height SDS, and Height Velocity at Each Visit
16.2.6.1.b	Listing of antibodies and efficacy data in all patients in Study CP-4-004 OLE
16.2.6.2	Bone Age by Visit
16.2.6.3	Bone Maturation by Visit
16.2.7.1	All Adverse Events
16.2.7.2	All Serious Adverse Events
16.2.7.3	All Adverse Events Leading to Withdrawal from the Study
16.2.7.4	All Adverse Events of Special Interest
16.2.7.5	All Injection Site Reactions
16.2.8.1	IGF-1 and IGF-1 SDS Results at Each Visit
16.2.8.2	IGF-1 SDS > 2
16.2.8.3	IGFBP-3 Results at Each Visit
16.2.8.4	Glucose Metabolism Results
16.2.8.5	Endocrinology Results
16.2.8.6	Lipid Metabolism Results
16.2.8.7	Chemistry Results
16.2.8.8	Hematology Results
16.2.8.9	Urinalysis Results

Listing No.	Description
16.2.8.10	Pregnancy Test Results
16.2.8.11	Gonadotropic Hormone Results
16.2.8.12	MOD-4023 Serum Levels
16.2.9.1	Vital Sign Results by Visit
16.2.9.2	Physical Examination Results
16.2.9.3	Electrocardiogram Results
16.2.9.4	Concomitant Medications
16.2.9.5	Exposure and Duration of Treatment
16.2.9.6	Antibody Titers
16.2.9.6b	Antibody Titers (Anti-hGH Nab)
16.2.9.7	Injection Site Pain, Redness, Bruising, Swelling, and Itching Scores by Visit
16.2.9.8	Fundoscopy
16.2.9.9	Weight and Height at Each Visit
16.2.9.10	Pubertal Status by Visit
16.2.9.11	Summary of Dose Adjustments
16.2.9.12	Listing of antibodies to somatrogon and individual efficacy data in patients with CTP+ in Study CP-4-004 (Main and OLE)

11.3 Figures

Figure No.	Description
7	Height SDS and Cumulative Change in Height SDS by Year and by ADA Status in Study (All Cohorts Combined)
8	IGF-1 SDS by Year by ADA Status in Study
14.2.1.1&2	Annualized Height Velocity
14.2.1.3	Summary of Annualized Height Velocity for All Cohorts Combined at Each Year of Study
14.2.2.2A	Summary of Height SDS by Initial Cohort Assignment at Each Year of Study
14.2.2.2B	Summary of Height SDS by Year of Study and Initial Cohort Assignment
14.2.2.2C	Summary of Height SDS for All Cohorts Combined at Each Year of Study
14.3.5.1	IGF-1 SDS
14.4.2.1&2	Annualized Height Velocity by ADA Status
14.4.2.3	Summary of Annualized Height Velocity for All Cohorts Combined at Each Year of Study by ADA Status
14.4.2.5&8	Summary of Height SDS for All Cohorts Combined at Each Year of Study by ADA Status
14.4.2.9	Peak IGF-1 SDS by ADA Status
14.5.1.1	Clinical Laboratory Summary: Glucose Metabolism
14.5.2.1	Clinical Laboratory Summary: Endocrinology

Figure No.	Description
14.5.3.1	Clinical Laboratory Summary: Lipid Profile
14.5.4.1	Clinical Laboratory Summary: Chemistry
14.5.5.1	Clinical Laboratory Summary: Hematology
14.5.6.1	Clinical Laboratory Summary: Urinalysis
16.2.8.7	Maximum Bilirubin Versus Maximum ALT and AST

Signature Page for CP-4-004 OLE SAP v6.0

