3.1.2 Secondary Objectives

The secondary objective is to evaluate the growth outcome of somatrogon in long term treatment beyond the initial 12 months of the primary study, including the transition to PEN to the EOS.

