9.13 Extent of Exposure

The total duration of treatment (in months) for each patient will be calculated as:

- 1. The total duration since first treatment in this study (since the first dose of Period I)
 - a. For patients initially randomized to Genotropin, the total duration of exposure to somatrogon will be calculated from the date for first treatment with somatrogon.
- 2. The total duration in each assigned dose level and on PEN.
- 3. The overall exposure will be calculated as Last dose First dose + 7 days (to account for the once weekly dose exposure). To convert to months, the total daily exposure will be divided by 30.147.

Because of potential gaps in treatment between periods, the total duration may not represent continuous exposure. A listing of the patients with gaps in treatment will be provided showing the time period without treatment.

The number and proportion of patients who have the dose adjusted due to IGF-1 SDS >2 or other reasons will be summarized by reason for each 12 month period, with the denominator as the number of patients who started each period. The listings will show the dose at which the IGF-1 SDS excursion occurred.

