10 GROWTH OUTCOMES

10.1 Annualized HV

Descriptive statistics or HT will be presented. Annualized HV between two time intervals X and Y will be calculated as:

$$\begin{aligned} \text{Height Velocity} & \left(\frac{cm}{year}\right) \\ &= \left[\frac{\text{Month X Height (cm)} - \text{Reference Month Y Height (cm)}}{\text{Month X date} - \text{Reference Month Y date}}\right] * 365.25 \end{aligned}$$

HV will be calculated for the following intervals:

- 1. Periods III and IV
 - a. 12 month intervals, with the first 12 months starting with the first injection of Period III. Gaps in treatment will not alter that calculation of these 12 month intervals.
 - b. Last 6 and 12 month interval, using the last measure in Period IV with the measures at 6 and 12 months prior to the last measure as the reference.
- 2. Period V (PEN)
 - a. Intervals of 6 and 12 months from the start of the PEN injection as the reference for the first year.
 - b. After the first year of PEN, HV at the end of each year uses the measure at the Month 12 visit in each year with the measure at the Month 12 visit of the prior year as the reference. In cases where there is a gap in treatment between years, the measure at the restart of treatment (if available) will be used as the reference.

HV will also be presented for each treatment year, including Periods I and II, by the original treatment group assignment.

For patients who discontinue from the study between these specific defined visits for the calculations, their last HT measurement and date will be used for the annualized HV in the interval of interest.

Annualized HV by year, annualized HV on PEN treatment, change in HT SDS by year and change in HT SDS on PEN treatment will be summarized by ADA status.

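### The pooled all-cohort growth summaries include the Genotropin cohort's Main Study year, and their ADA-split versions have no rule for patients not tested for anti-somatrogon antibody that year

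*SAP*

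**What the plan says.** The growth objective in SAP 3.1.2 is "to evaluate the growth outcome of somatrogon in long term treatment beyond the initial 12 months of the primary study". SAP 5 puts all extension patients in one Full Analysis Set.

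For height SDS, SAP 10.3 states: "HT SDS will also be presented for each treatment year, including Period I and II, by the original treatment group assignment and total". It adds that "the cumulative change in HT SDS from the baseline at Period I will be calculated" at each scheduled Month 12 visit, again by initial group and total.

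For height velocity, SAP 10.1 states: "HV will also be presented for each treatment year, including Periods I and II, by the original treatment group assignment". No total is mentioned there. The pooling appears only in the figure list of SAP 11.3, which includes "Summary of Annualized Height Velocity for All Cohorts Combined at Each Year of Study" (Figure 14.2.1.3). The same list has a pooled height SDS figure (14.2.2.2C) and pooled ADA-split figures (7, 14.4.2.3, 14.4.2.5&8).

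For exposure, SAP 9.13 treats the former Genotropin patients separately: "For patients initially randomized to Genotropin, the total duration of exposure to somatrogon will be calculated from the date for first treatment with somatrogon". Section 10 has no matching rule for growth.

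On antibodies, SAP 1 defines ADA as anti-somatrogon antibody. SAP 9.2 assigns status on a rolling basis: a patient counts as positive from the start of the year of a positive test and stays positive. The protocol (Section 5.1.2 and Appendix 1) schedules anti-MOD-4023 testing in the Main Study for Cohorts 1-3 only; Cohort 4 is tested for anti-hGH.

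**The concern.** Cohort 4 received no somatrogon until Period III. A combined value for the Main Study year therefore averages three somatrogon doses with the active control. Any combined change measured from Period I baseline carries Cohort 4's comparator-year gain for as long as those patients contribute.

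The ADA-split versions add a second difficulty. A patient who has not been tested for anti-somatrogon antibody cannot become positive under SAP 9.2, and the rule has no third category. If Cohort 4 is left in the non-positive group, the year-1 comparison of growth by antibody status is partly a comparison of drugs. That matters because these figures are the ones a reader would use to judge whether antibodies affect growth.

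**Working it through.** The plan states no figure for this point and has no hypothesis test for the extension (SAP 4.1, 7.1), so there is nothing to reproduce. The check is a trace through the text, then simple shares.

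**Which outputs contain the Genotropin year**

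| Output | Main Study year | Later years |
|---|---|---|
| Pooled height velocity (Figures 14.2.1.3, 14.4.2.3) | Includes Genotropin growth | All growth is on somatrogon |
| Pooled height SDS and cumulative change (SAP 10.3 total; Figures 7, 14.2.2.2C, 14.4.2.5&8) | Includes Genotropin growth | Genotropin-year gain persists |
| By-cohort tables (e.g. 14.2.1.3, 14.2.2.2, 14.2.3.3) | Cohort 4 shown separately | Cohort 4 shown separately |
| Annual velocity and annual change tables for extension and PEN years (14.2.1.1, 14.2.1.2, 14.2.3.1, 14.2.3.2) | Not included | Unaffected |

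Tables 14.4.2.3, 14.4.2.5 and 14.4.2.8 report ADA status by cohort at the end of the Main Study, so ADA status is applied to that year.

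**Inputs**
- Planned: up to 56 patients, 14 per cohort, randomised 1:1:1:1 (protocol synopsis and 4.5).
- Entered the extension: 53 (SAP 4.1). The number from Cohort 4, *g*, is not given.
- Assumption: all 56 were enrolled at 14 per cohort, so 3 did not continue and *g* lies between 11 and 14.
- Assumption: a share *p* of somatrogon patients is ADA-positive in year 1. The documents give no value; 0 to 0.5 is shown.
- *D* is the Genotropin mean minus the pooled somatrogon mean in year 1. The documents give no value.

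**Share of the pool**
- By design: 14/56 = 25%.
- In the extension set: 11/53 = 20.8% to 14/53 = 26.4%.

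**Shift in the combined year-1 mean** = (*g*/53) × *D*
- For each 1 cm/year of *D*: 0.21 to 0.26 cm/year.
- For *D* = 0.5: 0.10 to 0.13. For *D* = 2: 0.42 to 0.53. For *D* = 0: none.
- With no dropout, the same fraction of any year-1 difference in height SDS gain remains in the combined cumulative change at each later year.

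**Genotropin share of the year-1 non-positive group** = *g* / [*g* + (53 − *g*)(1 − *p*)]

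| *p* | *g* = 11 | *g* = 14 |
|---|---|---|
| 0 | 11/53 = 20.8% | 14/53 = 26.4% |
| 0.3 | 11/(11 + 29.4) = 27.2% | 14/(14 + 27.3) = 33.9% |
| 0.5 | 11/(11 + 21) = 34.4% | 14/(14 + 19.5) = 41.8% |

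**After Cohort 4 is left out**, the pool is 53 − 14 = 39 to 53 − 11 = 42 patients, and both Genotropin shares are zero.

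**The case against.** The strongest reply is that these outputs are supplementary, descriptive and openly titled as combining all cohorts. A reader might infer that the SAP presents them as somatrogon results, but no text labels them so. The objective concerns growth after the first 12 months, and the annual velocity and annual change tables that serve it contain no Genotropin-year growth. The by-cohort tables and patient listings let a reader separate Cohort 4. All of this stands and limits the point. It does not repair the combined figures, which are separate outputs with no footnote or exclusion.

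A reader might also infer that the combined velocity figures cannot be used at any year. That is not supported: after the Main Study point, every interval is on somatrogon for everyone.

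Nor does the SAP state that Cohort 4 is ADA-negative. SAP 9.2 is silent on untested patients, its one explicit negative default concerns neutralizing antibodies, and SAP 7.4 says missing data are generally not imputed. Not assessed is therefore an available reading. What stands is an unstated rule whose default puts these patients with the non-positive group.

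It is likewise tempting to say that all later cumulative comparisons set ADA-positive somatrogon patients against Genotropin patients. The documents do not support that. Former Genotropin patients are tested for anti-somatrogon antibody in the extension (protocol Appendix 2) and can turn positive, so the comparator-year gain can sit in either group.

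Lastly, protocol 1.4.1 describes growth on 0.66 mg/kg/week as comparable to Genotropin, which would argue for a small *D*. It reports no growth result for the two lower doses, which are also in the pool.

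**Conclusion.** The point holds in a limited form. The SAP 10.3 total and Figures 7, 14.2.1.3, 14.2.2.2C, 14.4.2.3 and 14.4.2.5&8 include one comparator year for about a quarter of the pool. Pooled velocity is affected at one time point; pooled height SDS and cumulative change from Period I baseline are affected throughout. The year-1 ADA comparison is partly somatrogon against comparator unless untested patients are set aside. With 30-50% of somatrogon patients ADA-positive, about 27-42% of the non-positive group would be Genotropin patients.

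The design share of 25% comes from the protocol. The 21-26% range assumes full enrolment, and the ADA shares also assume *p*. No cohort means are given, so neither the direction nor the size of any bias can be determined, and it could be zero. No hypothesis test is affected. The change is still worth making, because the outputs mix treatments without saying so and the repair is cheap.

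**What to change.** In SAP 10.1, 10.3 and 11.3:

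- For the Main Study year, and for height SDS and cumulative change from Period I baseline, pool Cohorts 1-3 only.
- Show Cohort 4 as its own line, and give its change from its OLE Day 1 value as well.
- Leave pooled height velocity for extension and PEN years as it is, on the study-year axis.

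In SAP 9.2 and the ADA-split outputs:

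- Class Cohort 4 as not assessed for ADA in the Main Study year and leave it out of ADA-split outputs for that year.
- Leave it out of ADA-split cumulative change based on Period I baseline.

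Re-aligning all patients on first somatrogon dose, by analogy with SAP 9.13, is not advised. It would set Cohort 4's second year of growth hormone beside the first year of treatment-naive patients. SAP 9.13 itself also reports duration from the first Period I dose.

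The cost is SAP wording and a re-run of a few descriptive tables and figures from existing data. The affected pooled summaries fall from 53 to about 39-42 patients.
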